2 INTRODUCTION

See Section 2 of the PROVENT CSP for the parent study and the AZD7442 IB.

2.1 Study Rationale

AZD7442, a combination of 2 mAbs (AZD8895 and AZD1061), is being evaluated for the prevention or treatment of COVID-19. PROVENT is an ongoing Phase III, randomized, double-blind, placebo-controlled, multi-center study in adults to assess the safety and efficacy of a single dose of AZD7442 for pre-exposure prophylaxis of COVID-19 (PROVENT parent study). This PROVENT sub-study will assess the safety, PK, and immunogenicity of repeat doses of AZD7442 in participants currently enrolled in the PROVENT study who may benefit from a repeat dose of AZD7442. This study will investigate whether additional doses of AZD7442 have an appropriate safety profile in this vulnerable population. Pharmacokinetic data will also be generated to evaluate whether repeat dosing can maintain serum concentrations of AZD7442 associated with protection against COVID-19.

2.2 Background

See Section 2.2 of the PROVENT CSP for the parent study.

2.3 Benefit/Risk Assessment

More detailed information about the known and expected benefits and potential risks of AZD7442 can be found in the AZD7442 IB.

2.3.1 Risk Assessment

Based on all available clinical study data with a cut-off date of 20 August 2021, there were no identified risks associated with AZD7442. The current risk assessment for AZD7442 is summarized in Table 6.

Table 6 Risk Assessment for AZD7442

Important Identified Risks	None
Identified Risks	None
Important Potential Risks	None
Potential Risks	Potential risks include injection-related reactions, ADE disease, serious hypersensitivity including anaphylaxis, and cardiac and thromboembolic events.
Reference Safety Information	For AZD7442, no SARs have been identified. Any SAE that is deemed to be related to the IP by the Investigator or the Sponsor will be treated as a suspected unexpected serious adverse reaction and appropriately expedited.

Based on a data cut-off of 20 August 2021.

ADE, antibody-dependent enhancement of disease; IP, investigational product; SAE, serious adverse event; SAR, serious adverse reaction.

In the PROVENT parent study, AZD7442 was generally well tolerated and preliminary analyses showed that overall AEs were balanced between the placebo and AZD7442 groups. A small number of cardiovascular serious adverse events (myocardial infarction and cardiac failure) have been reported in the PROVENT parent study at a higher rate in participants who received AZD7442 compared to placebo. All participants who experienced cardiac SAEs were at high risk for cardiac events, many of whom had a prior history of cardiovascular disease at baseline. There was no clear temporal pattern and a causal relationship between AZD7442 and these events has not been established. There was no signal for cardiac toxicity or thrombotic events identified in the nonclinical studies. Monitoring of cardiovascular events will occur in this sub-study. There were no cases of severe COVID-19 or COVID-19-related deaths in those treated with AZD7442. In the placebo arm, there were 3 cases of severe COVID-19, which included 2 deaths.

In a separate Phase III AZD7442 study STORM CHASER (N = 1121), which enrolled a younger population with fewer baseline cardiac risk factors than PROVENT and no related cardiac SAEs at the time of primary analysis.

2.3.2 Benefit Assessment

The PROVENT primary analysis showed that AZD7442 achieved a statistically significant reduction in the incidence of symptomatic COVID-19, the study's primary endpoint. AZD7442 reduced the risk of developing symptomatic COVID-19 by 77% (95% CI: 46, 90), compared to placebo. The study accrued 25 cases of symptomatic COVID-19 at the primary analysis.

The participants included in this PROVENT sub-study are those most likely to benefit from repeat doses of AZD7442 for ongoing protection against COVID-19.

2.3.3 Overall Benefit: Risk Conclusion

Taking into account the measures taken to minimize risk to participants in this sub-study, the potential risks identified in association with AZD7442 are justified by the anticipated benefits that may be afforded to participants at risk of COVID-19.

3 OBJECTIVES AND ENDPOINTS

Table 7 lists the objectives and endpoints for the PROVENT repeat dose sub-study.

Table 7 Objectives and Endpoints for Repeat Dose Sub-Study

Objective	Endpoint
Primary	
To evaluate the safety and tolerability of repeat doses of AZD7442 300 mg and 600 mg IM	AEs, SAEs, MAAEs, and AESIs post repeat dose of IMP
Secondary	
To evaluate the pharmacokinetics of repeat doses of AZD7442 300 mg and 600 mg IM	Serum AZD7442 concentrations following repeat dosing. PK parameters if data permit following repeat dosing
To evaluate ADA responses to repeat doses of AZD7442 300 mg and 600 mg IM in serum	Incidence of ADA to repeat doses of AZD7442 in serum
To determine anti-SARS-CoV-2 nAb levels in serum following repeat doses of AZD7442 300 mg and 600 mg IM	Post-treatment GMTs and GMFRs from baseline values after a repeat IM dose in SARS-CoV-2 nAbs (wild-type assay or pseudo-neutralization assay)
Exploratory	
PPD	PPD

ADA, antidrug antibody; AE, adverse event; AESI, adverse event of special interest; COVID-19, coronavirus disease 2019; GMT, geometric mean titers; GMFR, geometric mean fold rise; IM, intramuscular; IMP, investigational medicinal product; MAAE, medically attended adverse event; nAb, neutralizing antibody; PK, pharmacokinetic; RT-PCR, reverse transcriptase polymerase chain reaction; SAE, serious adverse event; SARS-CoV-2, severe acute respiratory syndrome-coronavirus 2.

4 STUDY DESIGN

4.1 Overall Design

This is a Phase III, multi-country, multi-center, open-label, PROVENT sub-study assessing the safety, PK, and immunogenicity (ADA) of repeat doses of AZD7442. Participants at a subset

of active PROVENT parent study sites in participating countries will be invited to enroll in this sub-study.

Participants will be adults who have been randomized and are actively participating in the PROVENT parent study who may benefit from a repeat dose of AZD7442. The aim is to approximately balance the proportion of participants derived from each of the AZD7442 and placebo arms from the double-blind parent study. If an imbalance between the arms is observed, a cap may be introduced.

There is no screening period in the sub-study and participants will retain their subject identification number from the parent study.

Participants will be eligible for inclusion in the sub-study once they have reached 12 ± 2 months post dose of IMP in the double-blind parent study. Eligible participants who have already completed their Day 366 Visit in the parent study will be unblinded, assigned to a sub-study group, and then undergo the SS-D1 assessments. For participants who have not yet completed their Day 366 Visit in the parent study, the SS-D1 visit will include the Day 366 assessments. Pre-dose Day 366 assessments will serve as baseline assessments for the sub-study.

All participants will receive additional doses of AZD7442 in the repeat dose sub-study (Figure 1). Initially, participants will be assigned to one of two dosing interval groups as follows:

- Group 1 (~ 12-month repeat dose interval): Participants who received AZD7442 300 mg IM on Day 1 of the parent study will receive their second dose of AZD7442 300 mg IM on SS-D1.
- Group 2 (~ 6-month repeat dose interval): Participants who received placebo on Day 1 in the parent study will receive their first dose of AZD7442 300 mg IM on SS-D1 followed by a second dose on SS-D183.

At 6 months (SS-D183), a subset of participants from USA sites in Group 1 and Group 2 who consent to receive additional AZD7442 600 mg doses (approximately evenly distributed between groups) approximately every 6 months and will be assigned to a new arm - Group 3. All other participants will continue in the sub-study according to their originally assigned dosing interval group schedule. The addition of Group 3 will create 4 possible dosing cohorts, based on the how many doses of 300mg AZD7442 received prior to entering Group 3 and whether or not this was followed by a further two doses of 600mg AZD7442:

Group 1

Cohort 1: AZD7442 300 mg, 300 mg

Group 2

Cohort 2: Placebo, AZD7442 300mg, 300 mg

Group 3

- Cohort 3 (from Group 1): AZD7442 300 mg, 300 mg, 600 mg, 600 mg
- Cohort 4 (From Group 2): Placebo, AZD7442 300 mg, 600 mg, 600 mg

Group level recruitment caps may be placed to ensure 50 or more participants complete the study with their assigned dose and valid samples.

Group 1 and Group 2 will undergo safety follow-up for 456 days after the last dose of AZD7442, and Group 3 will undergo safety follow-up for 183 days after the last dose of AZD7442. The total duration of the sub-study will be 457 days for Group 1, 639 days for Group 2, and 548 days for Group 3.

4.2 Scientific Rationale for Study Design

This sub-study of the ongoing PROVENT parent study was designed to rapidly obtain clinical safety, PK, and immunogenicity data after repeat AZD7442 dosing in individuals who cannot receive a COVID-19 vaccine or are not expected to be adequately protected by a vaccine (ie, the target population for repeat dosing). This sub-study will aim to enrich the PROVENT study population with individuals who may benefit from a repeat dose of AZD7442 by targeting appropriate participant groups enrolled in the parent study (see Section 5.1).

The dosing intervals of approximately 6 months and 12 months to be evaluated in this study are based upon the extended half-life of AZD7442 and expected need for repeat dosing in clinical practice.

To generate repeat dose data as rapidly as possible, participants randomized to the PROVENT parent study who meet the sub-study inclusion criteria will be offered participation in the sub-study when it is initiated. This will result in some participants receiving a repeat dose as early as 10 months after the first dose in the parent study.

- Participants assigned to the 12-month dosing interval (Group 1) will be derived from the AZD7442 arm in the parent study. These participants will enter the sub-study and receive their second dose 12 ± 2 months after receiving their first dose in the parent study, (see Figure 1). An interim analysis will take place when a minimum of 50 participants have been followed until Day 29.
- Participants assigned to the 6-month dosing interval (Group 2) will be derived from the
 placebo arm in the parent study. This group will receive their first dose of AZD7442 upon
 entering the sub-study followed by a repeat dose at approximately 6 months (see

Figure 1). This group will generate data supporting assessment of a shorter repeat dosing time interval of the long-acting AZD7442 formulation.

• Participants assigned to the 18-month dosing schedule (Group 3) will be derived from a subset of participants at the USA sites in Group 1 and Group 2 in the sub-study (approximately evenly distributed between groups). This group will receive 2 doses of 600 mg IM AZD7442 at approximately 6 month intervals starting at SS-D183, following consent to the amended sub-study (see Figure 1), to align the dosing schedule per the FDA Fact sheet. This group will generate additional safety, PK, and immunogenicity data for longer-term repeat dosing time intervals of the long-acting AZD7442 formulation.

Evaluation of the safety, PK, and ADA immunogenicity of repeat dosing with AZD7442 will inform the following:

- Whether repeat dosing at different dosing intervals will maintain the serum concentrations of AZD7442 associated with protection against symptomatic disease in the parent study.
- Whether the safety profile and immunogenicity (ADA) profile after a repeat AZD7442 dose are comparable to the safety profile and immunogenicity profile observed after a single AZD7442 dose.

To provide safety data on AZD7442 for 5 half-lives, safety endpoints will be collected for 456 days after the last dose of IMP in Group 1 and Group 2.

4.3 Justification for Dose

The dose level, 300 mg IM, selected for this sub-study is based on the dose administered in the PROVENT parent study which demonstrated a favorable safety and efficacy profile in the primary analysis and is the proposed dose to be marketed (see Section 2.3). For further details on the dose justification, please refer to the AZD7442 IB.

The 600 mg IM dose selected for this sub-study extension is based on the 600 mg dose administered in the TACKLE study, and 600 mg AZD7442 is authorized for emergency use in the USA since 24 February 2022; both of which were considered generally safe and well-tolerated.

4.4 Justification for Study Population

In the PROVENT parent study, more than 75% of participants have co-morbidities, which includes those with a reduced immune response to vaccination. The primary analysis showed that AZD7442 was well tolerated, and AEs were balanced between the placebo and AZD7442 groups.

The PROVENT sub-study targets the study population most likely to benefit from receipt of a repeat dose of AZD7442. Participants will be eligible to enter the sub-study and the additional

Group 3, if they fulfill at least one of the following criteria: (a) immunocompromised and/or may be at increased risk for an inadequate response to a COVID-19 vaccination; (b), in the opinion of the Investigator, are at increased risk of severe COVID-19 (including participants who have not received a COVID-19 vaccine) (see Section 5.1).

4.5 End of Study Definition

A participant is considered to have completed the sub-study if they completed all phases of the study, including the last scheduled procedure shown in the SoA (see Section 1.3).

The end of the sub-study is defined as the date of the last scheduled procedure shown in the SoA (see Section 1.3) for the last participant in the study globally.

5 STUDY POPULATION

Planned protocol deviations are not considered acceptable. A protocol deviation that is suspected or known to have the potential to significantly impact a participant's safety, physical or mental integrity, or scientific value will be classified as a serious breach.

5.1 Inclusion Criteria

Participants are eligible to be included in the sub-study if all the following criteria apply:

- 1 The participant has been randomized, dosed, and is ongoing in the PROVENT parent study and is 12 ± 2 months post first dose of blinded IMP.
- 2 If one or more of the following apply:
 - (a) Immunocompromised and/or may be at increased risk for an inadequate immune response to a COVID-19 vaccine, including:
 - o Elderly, ie, \geq 60 years old
 - Obese, ie, Body Mass Index≥ 30
 - Congestive heart failure
 - Chronic lung disease
 - Chronic kidney disease, ie, GFR < 30 mL/min/1.73 m² (Lamb et al 2013)
 - Chronic liver disease
 - Immunocompromised state from solid organ transplant, blood or bone marrow transplant, immune deficiencies, human immunodeficiency virus, use of corticosteroids, or use of other immunosuppressive medicines
 - Intolerant of vaccine. Defined as previous history of severe AE or SAE after receiving any approved vaccine.
 - (b) In the opinion of the Investigator, are at increased risk and would benefit from a repeat dose of AZD7442 (eg, participants who have a chronic condition that increases

their risk of severe COVID-19 or those who have not been vaccinated against COVID-19).

- Medically stable defined as disease not requiring significant change in therapy or hospitalization for worsening disease during the one month prior to enrollment to the substudy, with no acute change in condition at the time of sub-study enrollment as judged by the Investigator. This includes conditions newly diagnosed since the participant entered the parent study.
- 4 Documented negative SARS-CoV-2 RT-PCR test collected ≤ 3 days prior to SS-D1 or a negative rapid SARS-CoV-2 antigen test at screening.

Reproduction

- 5 Contraceptive use by men or women:
 - (a) Male Participants: Contraception for male participants is not required, however, to avoid the transfer of any fluids, all male participants must use a condom from SS-D1 and agree to continue through 365 days following administration of the IMP.
 - (b) Female Participants:
 - Women not of childbearing potential are defined as women who are either permanently sterilized (hysterectomy, bilateral oophorectomy, or bilateral salpingectomy), or who are postmenopausal. Women will be considered postmenopausal if they have been amenorrhoeic for 12 months prior to the planned date of randomization without an alternative medical cause. The following age-specific requirements apply:
 - Women < 50 years old would be considered postmenopausal if they have been amenorrhoeic for 12 months or more following cessation of exogenous hormonal treatment and FSH levels in the postmenopausal range.
 - Women ≥ 50 years old would be considered postmenopausal if they have been amenorrhoeic for 12 months or more following cessation of all exogenous hormonal treatment.
 - Female participants of childbearing potential must use one highly effective form of birth control. A highly effective method of contraception is defined as one that can achieve a failure rate of less than 1% per year when used consistently and correctly. Women of childbearing potential who are sexually active with a non-sterilized male partner must agree to use one highly effective method of birth control, as defined below, from SS-D1 and agree to continue through 365 days following administration of the IMP. Cessation of contraception after this point should be discussed with a responsible physician. Periodic abstinence (calendar, symptothermal, post-ovulation methods), withdrawal (coitus interruptus), spermicides only, and lactational amenorrhea method are not acceptable methods of contraception. Female condom and male condom should not be used together.

All women of childbearing potential must have a negative urine pregnancy test result before dosing at Visit SS-D1 and at SS-D183 as indicated in the SoA (see Section 1.3).

Examples of highly effective birth control methods are listed in Table 8.

Table 8 Highly Effective Methods of Contraception

Barrier Methods		Hormonal Methods		
Intrauterine device Intrauterine hormon (IUS) a Bilateral tubal occlu Vasectomized partn Sexual abstinence c	usion ner ^b	horr ovu ° ° Prog	nbined (estrogen- and progestogen-containing monal contraception) associated with inhibition of lation Oral (combined pill) Intravaginal Injectable Transdermal (patch) gestogen-only hormonal contraception associated inhibition of ovulation Oral Injectable Implantable	

This is also considered a hormonal method.

5.2 Exclusion Criteria

Participants are to be excluded from the study if any of the following criteria apply:

- 1 Have received a COVID-19 vaccination ≤ 14 days before SS-D1 or plan to receive a COVID-19 vaccination ≤ 14 days after SS-D1. (Such participants can subsequently be included in the study once they have reached > 14 days after their last dose of vaccine).
- 2 Have 2 or more untreated cardiac risk factors or suspected unstable cardiac disease.
- 3 Judgment by the Investigator that the participant should not participate in the study if the participant is unlikely to comply with study procedures, restrictions, and requirements.

5.3 Lifestyle Considerations

Lifestyle considerations for the sub-study are consistent with those in the parent study. See Section 5.3 in the PROVENT CSP for details.

Provided the partner is the sole sexual partner of the woman of childbearing potential study participant and that the vasectomized partner has received medical assessment of the surgical success.

Sexual abstinence is considered a highly effective method only if defined as refraining from heterosexual intercourse during the entire period of the study and if it is the preferred and usual lifestyle of the participant.

5.4 Screen Failures

Not applicable. See Section 5.2 for guidance on COVID-19 vaccinations.

6 STUDY INTERVENTION

The IMP is defined as any investigational intervention(s) or authorized product(s) intended to be administered to or medical device(s) utilized by a study participant according to the study protocol.

6.1 IMP(s) Administered

6.1.1 IMP

The majority of participants will receive at least one dose of 300 mg dose of AZD7442 (divided in 2 sequential injections, one for each mAb component) administered IM (Table 9). Participants who were randomized to AZD7442 in the parent study (Group 1) received their first dose of AZD7442 on Day 1 of the parent study and will receive their second dose on SS-D1 in the sub-study. Participants who were randomized to placebo in the parent study (Group 2) will receive their first and second AZD7442 doses on SS-D1 and SS-D183 of the sub-study, respectively.

Participants consenting to the sub-study extension amendment (Group 3) will receive 2 repeat doses of 600 mg IM AZD7442 at 6 month intervals.

A 300 mg and 600 mg dose of AZD7442 consists of 2 IM injections (one in each gluteal region). If a participant experiences an immediate hypersensitivity reaction after receipt of the first IM injection in the sub-study, but before the subsequent IM injections, further IMP should not be given. For details on the treatment of anaphylactic reactions after IMP IM injections see Appendix E. For further details on IMP discontinuation, see Section 7.1.

Table 9 Investigational Product

Intervention	300 mg AZD7442 (AZD8895 + AZD1061)	600 mg AZD7442 (AZD8895 + AZD1061)
name		
Dose	Liquid Product	Liquid Product
formulation	AZD7442 will be supplied as separate vials of AZD8895 and AZD1061 as 150 mg colorless to slightly yellow, clear to opalescent solutions for injection. The solutions contain 100 mg/mL of active ingredient (AZD8895 or AZD1061) in 20 mM L-histidine/L-histidine hydrochloride, 240 mM sucrose, and 0.04% (w/v) polysorbate 80, at pH 6.0. The label-claim volume is 1.5 mL.	AZD7442 will be supplied as separate vials of AZD8895 and AZD1061 as 300 mg colorless to slightly yellow, clear to opalescent solutions for injection. The solutions contain 100 mg/mL of active ingredient (AZD8895 or AZD1061) in 20 mM L-histidine/L-histidine hydrochloride, 240 mM sucrose, and 0.04% (w/v) polysorbate 80, at pH 6.0. The label-claim volume is 3.0 mL.
Unit dose strength(s)	300 mg AZD7442 consisting of 150 mg each of AZD8895 and AZD1061 at 100 mg/mL	600 mg AZD7442 consisting of 300 mg AZD8895 and 300 mg AZD1061 each at 100 mg/mL
Dosage level(s)	300 mg single dose of AZD7442 (150 mg of AZD8895 and 150 mg of AZD1061)	600 mg single dose of AZD7442 (300 mg of AZD8895 and 300 mg of AZD1061)
Route of administration	Two IM injections of 1.5 mL each (one in each gluteal region)	Two IM injections of 3 mL each (one in each gluteal region)
Use	Experimental	Experimental
Sourcing	AZD7442 (AZD8895 + AZD1061): AstraZeneca.	AZD7442 (AZD8895 + AZD1061): AstraZeneca
Packaging and labeling	IMP will be provided in glass vials. Each glass vial will be labeled as required per country requirement.	IMP will be provided in glass vials. Each glass vial will be labeled as required per country requirement.

IM, intramuscular; IMP, investigational medicinal product; w/v, weight per volume.

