6.2.1.3 Dose Preparation Steps

The 2 DPs AZD8895 and AZD1061 (comprising AZD7442), must both be administered separately to the participant in sequential order, with no participant receiving doses of AZD8895 without also receiving the matching dose of AZD1061. The dose of AZD8895 must be administered first. The dose of AZD8895 and AZD1061 for administration must be prepared by the IMP Manager or other qualified professional using aseptic technique, and who should only remove the required DP vials for participant dosing from storage. No incompatibilities have been observed between AZD7442 and disposable polypropylene or polycarbonate syringes used for IM administration.

Dose Preparation and Administration for AZD7442 (AZD8895/AZD1061)

The dose of AZD7442 (AZD8895 and AZD1061) for administration must be prepared by the Investigator's or site's designated IMP Manager using aseptic technique. Total time from needle puncture of the vial to the start of administration must not exceed:

- 24 hours at 2 °C to 8 °C (36 °F to 46 °F)
- 4 hours at room temperature.

If the final product is stored at both refrigerated and ambient temperatures, the total time must not exceed 24 hours, otherwise a new dose must be prepared from new vials. Each AZD8895

and AZD1061 vial must be used only once to prepare a single dose. AZD7442 (AZD8895 and AZD1061) does not contain preservatives, and any unused portion must be discarded.

A separate disposable syringe with a 22 to 25 gauge and 1 to 1.5 in (25 to 38 mm) length needle should be used for each AZD8895 and AZD1061 DP injection. Each DP should be administered as a separate single injection and administered sequentially. Intramuscular doses should be prepared by accurately withdrawing 1.5 mL volume of DP for Group 1 and Group 2 and 3.0 mL of DP for Group 3 into an appropriately sized latex-free disposable polypropylene or polycarbonate syringe. AZD8895 and AZD1061 should be administered according to standard practice procedures for IM injections, with one injection in each gluteal region. The IMP does not contain preservatives and any unused portion must be discarded.

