Appendix E Anaphylaxis

In adults, anaphylaxis is highly likely when any one of the following 3 criteria is fulfilled:

Acute onset of an illness (minutes to several hours) with involvement of the skin, mucosal tissue, or both (eg, generalized hives, pruritus or flushing, swollen lips, tongue and/or uvula)

AND AT LEAST ONE OF THE FOLLOWING:

- Respiratory compromise (eg, dyspnea, wheeze-bronchospasm, stridor, reduced peak expiratory flow, hypoxemia)
- Reduced BP (see number 3 below for definition) or associated symptoms of endorgan dysfunction (eg, hypotonia [collapse], syncope, incontinence)
- 2 Two or more of the following that occur rapidly after exposure to a likely allergen for that participant (minutes to several hours):
 - Involvement of the skin-mucosal tissue (eg, generalized hives, itch, flush, swollen lips, tongue and/or uvula)
 - Respiratory compromise (eg, dyspnea, wheeze-bronchospasm, stridor, reduced peak expiratory flow, hypoxemia)
 - Reduced BP (see number 3 below for definition) or associated symptoms (eg, hypotonia [collapse], syncope, incontinence)
 - Persistent gastrointestinal symptoms (eg, crampy abdominal pain, vomiting)
- Reduced BP after exposure to known allergen for that participant (minutes to several hours); for adults a systolic BP of less than 90 mmHg or greater than 30% decrease from that person's baseline BP (taken at or immediately prior to start of the IMP administration), whichever BP is lower.

The following definitions are provided for the purposes of this study:

Hypersensitivity reaction: An acute onset of an illness with involvement of the skin, mucosal tissue, or both after injection of IMP (but does not meet the definition of anaphylaxis described above).

To assist with the mitigation of these AEs, see Table 15, which categorizes reactions by severity of symptoms and proposes severity-specific treatment and offers guidance on management of IMP. Final treatment is at the discretion of the Investigator and should reflect local standard of care.

Table 15 An Approach to Management of Anaphylactic, Hypersensitivity, and Post-injection Reactions

Severity of symptoms	Treatment	Investigational product
Mild local reactions (During and post injection and hypersensitivity)	Evaluate participant, including close monitoring of vital signs.	Pause or hold additional IMP injection immediately.

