Mild injection site reactions such as redness, mild swelling, pain at the injection site or headache, nausea, non-pruritic rash, or mild hypersensitivity reactions including localized at the injection site or generalized cutaneous reactions such as mild pruritus, flushing, rash, dizziness, headache, ≤ 20 mmHg change in systolic BP from pre-administration measurement.	At the discretion of the Investigator, treat participant, for example, with: Localized cold pack or heat to the injection site. If more generalized reaction: Diphenhydramine 50 mg PO or equivalent and/or Acetaminophen 500 to 650 mg or equivalent dose of paracetamol and/or Topical antihistamines and/or low-potency topical corticosteroid preparations and/or Anti-nausea medication, as needed.	At the discretion of the Investigator, resume current IMP administration under observation.
Moderate reactions (during or immediately post injection) Injection site reaction such as those listed above under mild reactions but excluding moderate hypersensitivity reactions (see below).	Evaluate participant, including close monitoring of vital signs. Treat participant, for example, with: Normal saline (~500 to 1000 mL/hour IV) and/or Diphenhydramine 50 mg IV or equivalent and/or Acetaminophen 500 to 650 mg or equivalent dose of paracetamol and/or Anti-nausea and/or antiemetic intramuscular, as needed.	Stop or hold additional IMP administration immediately. At the discretion of the Investigator, resume current IMP administration under observation.

Table 15 An Approach to Management of Anaphylactic, Hypersensitivity, and Post-injection Reactions

Severity of symptoms	Treatment	Investigational product
Moderate hypersensitivity reactions Reactions which may include generalized rash or urticaria, palpitations, chest discomfort, shortness of breath, hypo- or hypertension with > 20 mmHg change in systolic BP from pre-infusion measurement.	Evaluate participant, including close monitoring of vital signs. Treat participant, for example, with: Normal saline (~500 to 1000 mL/hour IV) and/or Diphenhydramine 50 mg IV or equivalent and/or Acetaminophen 500 to 650 mg or equivalent dose of paracetamol and/or IV corticosteroids, such as hydrocortisone	Stop IMP administration immediately.
	100 mg or methylprednisolone 20 to 40 mg.	

Table 15 An Approach to Management of Anaphylactic, Hypersensitivity, and Post-injection Reactions

Severity of symptoms	Treatment	Investigational product

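### Section 6.1.1 rules out further IMP after an immediate hypersensitivity reaction to the first injection, with no severity limit, but the mild row of Table 15 allows dosing to resume, and nothing says which prevails

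*Protocol*

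**What the plan says.** Section 6.1.1 of the protocol describes each 300 mg or 600 mg dose as two intramuscular injections. Section 6.2.1.3 puts AZD8895 before AZD1061.

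On reactions between the two, Section 6.1.1 begins: "If a participant experiences an immediate hypersensitivity reaction after receipt of the first IM injection in the sub-study". It goes on to say that, if this is "before the subsequent IM injections, further IMP should not be given". It names no grade and no exception. Its pointer to Appendix E is limited to treatment: "For details on the treatment of anaphylactic reactions after IMP IM injections see Appendix E". For discontinuation it refers to Section 7.1.

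Appendix E defines the term without a severity floor, short of anaphylaxis: "Hypersensitivity reaction: An acute onset of an illness with involvement of the skin, mucosal tissue, or both after injection of IMP". Table 15 then sorts reactions by severity. Its mildest row is headed "Mild local reactions (During and post injection and hypersensitivity") and covers "mild hypersensitivity reactions including localized at the injection site or generalized cutaneous reactions such as mild pruritus, flushing, rash". The investigational-product column of that row first tells the site to hold the additional injection and then says: "At the discretion of the Investigator, resume current IMP administration under observation".

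Section 6.2.1.3 also asks for matched administration, "with no participant receiving doses of AZD8895 without also receiving the matching dose of AZD1061".

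**The concern.** A participant who develops mild generalized itching or a rash after AZD8895, before AZD1061 is given, meets the trigger in Section 6.1.1 and also falls in the mild row of Table 15. One passage says no further IMP. The other leaves the second injection to the investigator.

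What is at stake is consistent handling in a sub-study whose primary objective is the safety of repeat dosing. The instruction a site follows determines whether the participant is exposed to one antibody or both, and whether any worsening after the second injection can be observed. It also determines compliance. Section 5 does not accept planned deviations and Section 8 allows no waivers, so an investigator who relies on Table 15 in good faith would still be out of line with Section 6.1.1.

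**Working it through.** No sample size, rate or power figure is involved, so there is nothing to recompute. The check is a comparison of the passages.

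1. **Does Section 6.1.1 reach mild reactions?** Yes, as written. It sets no severity limit, and the Appendix E definition needs only acute skin or mucosal involvement after injection. Mild pruritus, flushing or rash meets that.

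2. **Does the mild row of Table 15 govern the same interval?** Yes. It tells the site to hold an additional injection, which makes sense only when one injection has been given and another is due. That is the interval in Section 6.1.1.

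3. **Where do the two agree and where do they differ?**

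| Table 15 row | Hypersensitivity? | Table 15 on the current dose | Section 6.1.1 | Result |
|---|---|---|---|---|
| Mild, hypersensitivity part | Yes | Hold, then may resume at investigator discretion | No further IMP | Conflict |
| Moderate reactions | No; moderate hypersensitivity is excluded from this row | Stop or hold, then may resume at discretion | Not triggered | No conflict |
| Moderate hypersensitivity | Yes | Stop, no option to resume | No further IMP | Agree |
| Severe or life-threatening | Yes | Stop, do not resume, discontinue permanently | No further IMP | Agree |

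   The conflict is one part of one row. The injection-site reactions, headache and nausea also listed in the mild row do not by themselves trigger Section 6.1.1.

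4. **Does any passage settle it?** No. Section 6.1.1 sends the reader to Appendix E for treating anaphylactic reactions, not for an exception to its own instruction. Section 7.1 contains no hypersensitivity criterion. Appendix E describes Table 15 as guidance on managing IMP but does not say that it yields to Section 6.1.1.

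5. **What is the scope in time?** Two phrases are open. Read literally, the first injection in the sub-study is the AZD8895 injection at SS-D1. On that reading Section 6.1.1 is silent on the SS-D183 dose (Groups 2 and 3) and the SS-D366 dose (Group 3), and Table 15 alone would apply there. Read as the first injection of any dose, Section 6.1.1 covers every dosing visit. Separately, the bar on further IMP could mean the rest of that dose or all later doses as well.

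6. **What of Section 6.2.1.3?** Stopping after AZD8895 leaves that participant without the matching AZD1061, and no exception is written. This follows equally from a stop under Section 6.1.1 and from the stop rows of Table 15, so it is a side effect of any mid-dose safety stop and separate from the conflict in step 3.

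**The case against.** The strongest reply is that the two passages can be followed together. Table 15 is guidance and resumption is discretionary, so a site that always withholds the second injection satisfies both. This is right as far as it goes. A reader might infer that sites are bound to treat the same patient in opposite ways, and the documents do not support that. They support only that sites could differ, because a site that uses the discretion departs from Section 6.1.1.

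A second reply concerns later doses. A reader might infer that dosing at SS-D183 or SS-D366 after a mild or moderate reaction is left without any rule, since only the severe row speaks of permanent discontinuation. Section 8 answers most of this: immediate safety concerns go to the sponsor to determine whether the participant continues IMP. What stands is narrower, namely that the wording of Section 6.1.1 does not show whether its own bar extends to those doses.

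A third reply is that the pairing sentence in Section 6.2.1.3 sits under dose preparation and describes routine administration, so a safety stop is naturally read as an exception. That is fair, and the point is secondary.

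A fourth reply is that the listed AESI is anaphylaxis and other serious hypersensitivity, whereas the conflict concerns mild reactions. These are recorded as adverse events whichever passage a site follows, and Section 9.1 states that no hypotheses will be tested. This also stands: no effect on a study conclusion has been shown. None of these replies removes the contradiction for the mild case.

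**Conclusion.** The inconsistency is real and narrow. For a mild hypersensitivity reaction between the two injections, Section 6.1.1 and the mild row of Table 15 give different instructions, and the protocol does not rank them. The passages must be reconciled because they bear on participant safety and on consistent exposure. It is a wording correction and does not put the analysis at risk.

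Its size is unknown. A reader might take the roughly 500 SS-D1 dosings, plus the later dosing visits, as the number affected. That counts opportunities. The affected group is participants with a mild hypersensitivity reaction in the short interval between two sequential injections, and neither document gives a rate for that. The nearest statement is in Section 18.1.2 of the SAP, which for the same two-injection dose in the parent study expects an adverse event that stops the second injection to be rare. That is not a rate for mild reactions and it concerns the parent study, but it supports regarding the number as probably small.

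The verdict assumes that the hypersensitivity reaction in Section 6.1.1 carries the Appendix E definition. If the sponsor intended a narrower meaning in Section 6.1.1, the text does not say so, and stating it would be one way to resolve the conflict.

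**What to change.** - Reconcile Section 6.1.1 and the mild row of Table 15 into one rule, worded identically in both places. Which rule that is remains a clinical decision for the sponsor; this review takes no view on it.
- In Section 6.1.1, state whether the first injection in the sub-study means SS-D1 only or the first injection at each dosing visit, and whether the bar on further IMP covers that visit only or later scheduled doses too. Keep this consistent with the sponsor-discussion process in Section 8.
- As a secondary wording point, note in Section 6.2.1.3 that a safety stop after AZD8895 is an exception to the pairing requirement.

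The cost is protocol wording and a memo to sites. No procedures, visits or samples are added.
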